"Impact of melatonin, food timing and receptor gene variant on type 2 diabetes risk"

Main researcher: [name]

Identifier: NCT03036592

Date: 09/01/2016

EXCLUSION CRITERIA

-Age between 18 and 70 years.
-No diabetes.
-Without any relevant medication use such as:

Diabetes-related medications
Growth hormones
Anti-coagulants
Beta-blockers
Hypnotics
Melatonin use or other sleep-related medications.

MEASUREMENTS

1. Habitual dinner timing:

In order to evaluate food habits, initial dietary intake will be determined by a 24-hour dietary recall in both populations at the initial screening. A smartphone application that transmits a time-stamp and photograph of each snack/meal taken during the 7 days and nights prior to the tests was used. This was supplemented with a 7-day food record.

2. Light exposure:

Light exposure was measured during the start of the early and late evening OGTTs. For the late evening OGTT, light intensity will be kept dim (0-25 lux), and for the early evening OGTT, light intensity will be kept bright ((\geq 450 lux).

3. Other traits:

- BMI
- Waist and Hip (cm)
- Sex, age

4. Melatonin at time of OGTT early and late:

Plasma melatonin will be measured 4 times per subjects at T0 and T120 during both OGTTs (2-time points x 2 OGTT) at the same laboratory by radioimmunoassay (RIA) (IBL, Germany). The intra- and inter-assay precision was 6.7% and 10.4% respectively.

5. Behavioral characteristics:

Physical activity will be assessed by the International Physical Activity Questionnaire (IPAQ) which determines physical activity over the last 7 days. Habitual weekday and weekend sleep timing and duration will be estimated by questionnaire and supplemented by 7-days of smartphone application.

6. OGTTs

A 75g OGTT will be performed twice on 750 participants, once in the early and once in the late evening. After an 8 hour fast, blood samples will be collected to measure glucose and insulin at 0 (fasting) and 30, 60, 90 and 120 minutes will be measured. Glucose will be measured using the Gluco-quant hexokinase test, COBAS Integra 400 (Roche, Indianapolis, IN) with a sensitivity of 2mg/dL and an intra- and interassay precision of 1.0% and 1.7%. Insulin was measured using the ECLIA ELECSYS test, COBAS e-801 (Roche Diagnostics GmbH, Mannheim, Germany) with a sensitivity of 0.2 ulU/ml and an intra- and interassay precision of 0.8-1.5% and 3.2-3.7%.

- 2 measures or conditions:
- Early: 4 h before their habitual bedtime.

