- Late: 1 h before their habitual bedtime (should come 1h before of the T0 and kept in the dim light condition). The samples will be just before the glucose T0 and at T30', T60', T 90'y T120' minutes after the glucose.

7. Biochemical determinations

- Glucose and insulin in the 5 times (T0, T30', T60', T 90'y T120')
- Melatonin in T0' and T120'

8. Statistical analysis plan

Postprandial glucose and insulin responses were estimated during the 120 minutes using incremental area under-the-curve (AUC) and were calculated by the trapezoidal method. An ANOVA of repeated measurements (ANOVArm) was used to compare glucose and insulin responses between early and late eating conditions. If significant, paired t-tests were performed to examine statistical significance between each OGTT time point. Insulin sensitivity was evaluated using the insulin sensitivity index (ISI) calculated from the OGTT data as 10,000/ (fasting glucose × fasting insulin × mean OGTT glucose × mean OGTT insulin)^{1/2}. Beta-cell function was assessed as the corrected insulin response (CIR) during the OGTT (100 × insulin30/ [glucose30 × (glucose30 – 3.89)]). Finally, the disposition index (DI) was calculated as a measure of insulin secretion in relation to insulin sensitivity (DI= ISI×CIR). Paired t-tests were performed to compare metrices in the two conditions.

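### The corrected insulin response (CIR) and disposition index (DI) are compared by paired t-test on the raw scale, with no glucose unit and no rule for 30-minute glucose near 3.89, where CIR breaks down

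*SAP*

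**What the plan says.** SAP section 8 (Statistical analysis plan) introduces CIR: "Beta-cell function was assessed as the corrected insulin response (CIR) during the OGTT". The formula is printed as "100 × insulin30/ [glucose30 × (glucose30 – 3.89" with the brackets then closed. DI follows: "Finally, the disposition index (DI) was calculated as a measure of insulin secretion in relation to insulin sensitivity", computed as ISI times CIR, where ISI is the insulin sensitivity index. The test for all three indices is given in one sentence: "Paired t-tests were performed to compare metrices in the two conditions".

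Neither document mentions a log or other transformation, a rank-based alternative, a unit for glucose in this formula, or what to do when glucose30 is at, near or below 3.89. The only glucose concentration unit in either document is in SAP section 6 (OGTTs), where it describes the assay: "with a sensitivity of 2mg/dL and an intra- and interassay precision of 1.0% and 1.7" percent. The same section gives the sample: "A 75g OGTT will be performed twice on 750 participants, once in the early and once in the late evening". Participants are non-diabetic under both documents.

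**The concern.** CIR has a pole: its denominator is zero at glucose30 = 3.89 and negative below. Values just above 3.89 are enormous and values just below are enormous and negative. A negative insulin response has no sensible reading. DI is a product with CIR, so it inherits both the pole and the sign.

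Followed literally in mmol/L, the plan puts such values straight into a mean difference, where a few participants can outweigh the rest. If glucose30 has any probability density at 3.89, the mean of raw CIR does not exist. The paired t-test then has no stable quantity to estimate, and a larger sample does not cure that. Away from the pole CIR is still right-skewed, which is a separate and milder reason to log it.

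At stake are the conclusions on beta-cell function and disposition index. If the rule for extreme or negative values is not written down beforehand, it will be chosen after they are seen.

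**Working it through.** The plan gives no power, effect size, SD or glucose30 distribution for these indices, so it has no figure to reproduce.

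**1. Unit.** 3.89 mmol/L × 18.016 = 70.1 mg/dL, so the constant fits mmol/L. If 8.0 mmol/L were entered as 144 mg/dL with 3.89 unchanged, then with insulin30 = 60, 6,000/(144 × 140.11) = 0.30 instead of 182. That is a different index, not a rescaling. The steps below use mmol/L.

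**2. The formula near 3.89.** CIR = 100 × I30/[G30 × (G30 − 3.89)]. The insulin values are illustrative.

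| G30 | I30 | Calculation | CIR |
|---|---|---|---|
| 8.00 | 60 | 6,000/(8.00 × 4.11) | 182 |
| 4.39 | 40 | 4,000/(4.39 × 0.50) | 1,822 |
| 3.95 | 40 | 4,000/(3.95 × 0.06) | 16,878 |
| 3.80 | 40 | 4,000/(3.80 × −0.09) | −11,696 |

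One value of 16,878 contributes 16,878/750 = 22.5 to the mean, or 12% of 182.

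**3. Assay error, using the SAP's own precision.** The relative change in CIR per relative change in G30 is (2G − 3.89)/(G − 3.89): 2.95 at 8.0, 9.78 at 4.39 and 66.8 at 3.95.
- At 4.39 the CIR error is 9.78 × 1.0% = 9.8% (intra-assay) or 9.78 × 1.7% = 16.6% (inter-assay).
- At 3.95 with 1.0%, ±1 SD is 3.9105 to 3.9895, and CIR (insulin30 40) runs from 49,897 down to 10,077.
- At 3.95 with 1.7%, ±1 SD is 3.883 to 4.017. This crosses 3.89, and CIR at the two ends is −144,080 and 7,831.

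**4. Power under assumed inputs.** Each scenario has 2,000 simulated trials of 750 pairs, two-sided 5% (simulation SE at most 1.1 points). None of the following comes from the documents: within-person correlation 0.6; insulin30 median 60 with log-SD 0.6; late condition +0.2 mmol/L glucose30 and −2% insulin30. At G30 = 8.0 that is a CIR ratio of 0.98 × (8.0 × 4.11)/(8.2 × 4.31) = 0.912, a fall of 8.8%. Raw and log tests have different targets, so power here means the chance of detecting this same shift.

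CIR power (%), as raw / raw after dropping pairs with G30 ≤ 4.39 / log. The first step shows the pole; the second shows general skew.

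| Assumed G30 (mean/SD) | Insulin–glucose correlation 0 | Correlation 0.4 |
|---|---|---|
| lognormal 8/1.0 | 94.7 / 94.7 / 98.6 | 99.8 / 99.8 / 100 |
| lognormal 9/1.4 | 83.0 / 83.0 / 93.0 | 97.4 / 97.4 / 99.5 |
| lognormal 8/1.4 | 82.9 / 86.4 / 96.8 | 96.6 / 99.2 / 99.8 |
| normal 8/1.0 | 86.8 / 90.4 / 98.6 | 98.4 / 99.6 / 100 |
| normal 9/1.4 | 54.4 / 69.1 / 90.9 | 82.0 / 94.1 / 99.2 |
| lognormal 8/1.7 | 44.8 / 74.4 / 93.2 | 68.6 / 96.4 / 99.2 |
| normal 8/1.4 | 18.6 / 70.5 / 95.4 | 33.4 / 93.9 / 99.5 |
| lognormal 7.5/1.7 | 14.8 / 74.3 / 95.4 | 25.4 / 96.2 / 99.6 |

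DI behaves alike. With ISI assumed lognormal (log-SD 0.5, correlation −0.5 with log insulin30, no change between conditions), the figures at correlation 0 are 96.8 / 96.8 / 99.0 for lognormal 8/1.0 and 17.8 / 73.8 / 96.4 for normal 8/1.4.

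**5. Direction and false positives (correlation 0).** The raw CIR mean difference had the wrong sign in 0%, 1% and 25% of trials (lognormal 8/1.0, lognormal 8/1.4, normal 8/1.4). With no true shift, the raw CIR test rejected in 4.3%, 5.2% and 2.2% of trials in the same order, and the log test in 4.4%, 5.8% and 4.4%.

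**The case against.** The strongest reply is that the pole may never be approached. Glucose30 is taken half an hour after a 75 g load, the documents do not show that low values are common, and in four of the eight scenarios at correlation 0 the pole costs 0 to 3.6 points. In the two with no pole effect, raw power is already 83–95%, and logging adds 4 to 10 points for a different target. With 750 pairs, a t-test on merely skewed data is defensible. All of this stands. The large losses are conditional illustrations, and the within-person correlation and effect size were not varied. It does not remove the need for a rule, because sample size offers no protection once values fall near 3.89.

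The unit gap is also mostly a one-line repair, since the constant points to mmol/L.

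Four stronger readings are tempting and not supported:
- *False positives.* A reader might infer an inflated error rate. The simulated raw test is near or below its nominal 5%.
- *Assay error always flips the sign at 3.95.* That holds with the 1.7% inter-assay figure but not with the 1.0% intra-assay figure. The SAP does not say whether a participant's two tests share a run. CIR is very unreliable there either way.
- *A positive insulin–glucose correlation cures the problem.* It raises raw power, but the part lost to the pole need not shrink. For normal 8/1.4 it grows from 70.5 − 18.6 = 51.9 points to 93.9 − 33.4 = 60.5. For normal 9/1.4 it falls from 14.7 to 12.1.
- *The other analyses fail too.* ISI, "10,000/ (fasting glucose × fasting insulin × mean OGTT glucose × mean OGTT insulin)^{1/2", has no such pole. The repeated-measures comparison, "An ANOVA of repeated measurements (ANOVArm) was used to compare glucose and insulin responses between early and late eating conditions", does not use CIR.

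**Conclusion.** The point holds, limited to CIR and DI. As written, the SAP applies a raw-scale paired t-test to an index that is undefined at glucose30 = 3.89 mmol/L, changes sign there and is dominated by assay error nearby. The arithmetic in steps 1 to 3 needs only the printed formula, the SAP's precision figures and illustrative insulin values. The consequence is lost power and an unstable estimate.

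How much is lost cannot be read from the documents. For CIR at insulin–glucose correlation 0, raw versus log power runs from 95% versus 99% (lognormal 8/1.0, skew only) to 19% versus 95% (normal 8/1.4) and 15% versus 95% (lognormal 7.5/1.7). Log power was higher in every scenario tabulated. This should be changed. Confidence is medium, because the practical size depends on an unknown glucose30 distribution.

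**What to change.** Amend SAP section 8 to:

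1. State that glucose enters CIR in mmol/L.
2. Set CIR and DI to missing when glucose30 is at or below 3.89 mmol/L, and report the number of such values by condition.
3. Analyse CIR and DI as within-person differences of logs, and report late/early geometric mean ratios with 95% confidence intervals.

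The rule in item 2 is needed alongside the log, which cannot take zero or negative values. A paired signed-rank test, or a sensitivity analysis excluding pairs with glucose30 within a pre-specified margin above 3.89, is optional. Once values are logged, dropping pairs at or below 4.39 moves power by at most 1.3 points, and the signed-rank test is no more powerful than the log t-test (94.6% versus 95.4% for normal 8/1.4). The margin without logs is only a partial repair, as the middle figures in the table show.

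The cost is wording and a transformation, with no new data. There are two downsides. The target becomes a ratio of geometric means rather than a mean difference. A few pairs also drop out on a post-glucose value: on average 0 to about 2.6 of 750 under the assumed scenarios, and not always evenly (normal 8/1.4: 1.2 early against 0.8 late). That is why the counts by condition must be shown.
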